3. SUMMARY OF STUDY PLAN

We propose to start with a pilot study that will test immunogenicity and safety of the vaccine in individuals at high risk for lung cancer. Even though the two trials described above have given us information about immunogenicity and safety of this vaccine in individuals at risk for colon cancer, we cannot assume the same for individuals at risk for lung cancer. We expect that smoking has led to the establishment of a long-term chronic inflammation in the lung of most potential participants, which is likely to lead to an increase in circulating MDSCs that could affect the response to the vaccine. Many of

the individuals eligible for the vaccine are expected to have ongoing chronic obstructive pulmonary disease (COPD), which has already been shown to expand numbers of circulating MDSCs creating an immunosuppressive microenvironment.³⁹ This does not allow us to predict either the rate of the immune response or the level of vaccine immunogenicity in this population. It is also possible that the extent of inflammation in the lung could make the lung more vulnerable to the effects of a strong adaptive immune response. Based on the safety profile of this vaccine in lung cancer trials, where the cancer-bearing lung is also a chronically inflamed organ, we do not expect any adverse effects. However, in none of these trials has very strong immunity been elicited by the vaccine. Thus, immunogenicity and safety have not yet been properly tested in this population. This pilot study will provide us with the safety and immunogenicity data that will decide whether testing of this vaccine could subsequently proceed to the placebo-controlled efficacy trial(s) for the prevention of lung cancer.

This is a pilot trial designed to evaluate co-primary endpoints: the preliminary immunogenicity in response to the MUC1 vaccine against abnormal MUC1 (assessed at 12 Weeks) and the safety (assessed at up to 24 weeks) in current and former smokers, who are at high risk for development of lung cancer. Immune response will also be evaluated at Week 24. We expect to consent and screen up to 85 participants in order to have approximately 40 evaluable participants with baseline and 12-week immunogenicity assessments. This includes a 41% rate of ineligibility and 20% rate of drop out/otherwise not evaluable. The projected rates of ineligibility, dropout, and otherwise not evaluable are based on experience with the prior MUC1 protocol and other engagements with the proposed target population. If the projected rates of ineligibility and drop out prove to be optimistic, it should be noted that even with 30 evaluable participants, statistical power will be sufficient for the purposes of this pilot study.

4. PARTICIPANT SELECTION

4.1 Pre-Registration Inclusion Criteria

- 4.1.1 Smoking history of ≥30 pack-years \underline{AND} either current smoker (still smoking or quit < 1 year prior to pre-registration) \underline{OR} former smoker (quit 1-15 years prior to pre-registration). Note: Pack years is determined by multiplying the number of packs smoked per day by the number of years smoked.
- 4.1.2 Ages 55-80 years
- 4.1.3 ECOG performance status ≤1 (See Appendix A)
- 4.1.4 CT scan of the chest done ≤ 6 months prior to pre-registration showing either negative findings (no nodules) OR solid or part-solid nodules < 6 mm in size OR consistent with < 1% probability of malignancy, Lung-RADs Version 1.0
- 4.1.5 Willingness to employ adequate contraception, if applicable. Note: the effects of MUC1/Poly-ICLC on the developing human fetus at the recommended therapeutic dose are unknown. For this reason, women of child-bearing potential and men must agree to use adequate contraception (hormonal or barrier method of birth control; abstinence) prior to study entry and for the duration of study participation. Should a woman become pregnant or suspect she is pregnant while participating in this study, she should inform her study physician immediately.

4.1.6 Ability to understand and the willingness to sign a written informed consent document

4.2 Pre-Registration Exclusion Criteria

- 4.2.1 History of any malignancy. Exceptions: Non-melanoma skin cancer or CIS of the cervix
- 4.2.2 Known Hepatitis B or C
- 4.2.3 Receiving any other investigational agents
- 4.2.4 Any prior investigational immune therapy, such as for lung cancer prevention or treatment or for CIS of the cervix
- 4.2.5 Use of oral or systemic steroids or other systemic anti-immune therapy ≤ 90 days prior to preregistration. Note: Use of inhaled/nasal steroids and local steroid injections for pain control are not exclusionary.
- 4.2.6 Known HIV
- 4.2.7 Known autoimmune disease
- 4.2.8 Known Non-alcoholic steatohepatitis (NASH) or Non-alcoholic fatty liver disease (NAFLD)
- 4.2.9 History of allergic reactions attributed to compounds of similar chemical or biologic composition to MUC1/Poly-ICLC
- 4.2.10 Uncontrolled intercurrent illness including, but not limited to, ongoing or active infection, symptomatic congestive heart failure, unstable angina pectoris, cardiac arrhythmia, or psychiatric illness/social situations that would limit compliance with study requirements.

4.3 Registration Inclusion Criteria

4.3.1 Participants must have normal organ and marrow function as defined below:

Leukocytes (WBC) \geq 3,000/microliterNeutrophils (ANC) \geq 1,500/microliterPlatelets \geq 100,000/microliter

Total bilirubin ≤ 1.5 x institutional upper limit of normal (ULN) Note: Higher

total bilirubin levels (≤ 3 mg/dL) can be allowed if due to known

benign liver condition, i.e. Gilbert's.

AST (SGOT) $\leq 1.5 \times \text{institutional upper limit of normal (ULN)}$ ALT (SGPT) $\leq 1.5 \times \text{institutional upper limit of normal (ULN)}$ Creatinine $\leq \text{institutional upper limit of normal (ULN)}$

4.4 Registration Exclusion Criteria

4.4.1 Any positive ANA titer above 1:160, even in an asymptomatic individual. Note: Weakly positive ANA defined as ANA titers up to 1:160 maximum (\leq 1:160) will be acceptable in an asymptomatic individual who is otherwise eligible for the study.

4.2.2 Pregnant or breast feeding. Note: Pregnant women are excluded from this study because the MUC1/Poly-ICLC vaccine may have the potential for teratogenic or abortifacient effects. Because there is an unknown but potential risk for AEs in nursing infants secondary to treatment of the mother with MUC1/Poly-ICLC vaccine, breastfeeding should be discontinued if the mother is treated with the vaccine.

4.5 Inclusion of Women and Minorities

Both men and women (as applicable) and members of all races and ethnic groups are eligible for this trial. Please refer to the Recruitment, Retention, and Adherence (RR&A) Plan for details.

4.6 Recruitment and Retention Plan

Each Participating Organization will be required to develop and submit a study- and site-specific RR&A plan for the purposes of insuring equal access to the clinical trial by individuals of all genders, races, and ethnic groups and for attaining the organization's accrual target. Participating Organizations will use the RR&A Plan Worksheet as the basis for their plans. At a minimum, these plans will be reviewed annually.

In summary, participants will be identified from the lung health, smoking, thoracic clinics, and/or CT screening programs at The University of Pittsburgh Medical Center and the Mayo Clinic in Rochester, Minnesota. Individuals at high risk for developing cancer but at low risk for having cancer will be recruited by the site study teams according to their site-specific RR&A plans and utilizing recruitment materials approved by NCI, DCP, the CIRB, and any applicable local entities. Accrual will be closely monitored by the Consortium Lead Organization and NCI, DCP. Accrual plans will be revised regularly and as needed to complete the study in an acceptable time frame.

5. AGENT ADMINISTRATION

Intervention will be administered on an outpatient basis. Reported adverse events (AEs) and potential risks are described in Section 6.2.

5.1 Dose Regimen and Dose Groups

The MUC1 peptide is manufactured at the FDA certified peptide facility of the University of Pittsburgh. The vaccine will consist of 100 micrograms of the MUC1 100mer peptide dissolved in 50 micro-liters of sterile saline, admixed with 500 micrograms of the adjuvant poly-ICLC (Hiltonol®) in 250 microliters volume, for a total injection volume of 300 microliters. Poly-ICLC is a TLR3 agonist, a synthetic, non-replicating dsRNA with no specific genetic message, which acts as a viral-mimic and activator of diverse elements of both the innate immune response and of adaptive immunity.⁴⁰

5.2 MUC1/Poly-ICLC Vaccine Administration

The vaccine will be administered by appropriate site personnel subcutaneously in the upper arm (preferably) or in the anterior thigh approximately 20 cm inferior to the inguinal ligament, if injection in the upper arm(s) is not possible. The vaccine will be administered into the same upper arm on all 3

occasions for vaccine delivery. The vaccine site may demonstrate erythema and/or tenderness after administration. This erythema and/or tenderness can persist even to the timing of the next vaccine dosing. Erythema is not a contraindication to repeat vaccination. However, persisting injection site tenderness (and/or other local injection site reaction) may, at the discretion of the investigator, be a reason to administer subsequent, scheduled vaccine into the opposite upper arm. Similarly, the 3rd vaccine administration can be given into the same upper arm as the previous (2nd) vaccine or into the opposite upper arm (the same upper arm where the initial 1st vaccine was given). Also, at the discretion of the investigator, repeat vaccination may be delayed, but not to exceed the protocol limits (See section 7.1). It is also possible to inject the vaccine into the thigh(s), if necessary.

5.3 Run-in Procedures

Not applicable.

5.4 Contraindications

If a study participant is prescribed corticosteroids, immunomodulators, or any medications listed as exclusionary (Section 4.2) during the course of the study, the participant will be taken off agent (no further vaccine administrations) but followed per protocol through the Follow Up telephone call.

5.5 Concomitant Medications

All medications (prescription and over-the-counter), and vitamin, herbal, and mineral supplements taken by the participant will be documented on the concomitant medication CRF and will include: start and stop date, dose and route of administration, and indication. Medications taken for a procedure (e.g., biopsy) will also be included.

5.6 Dose Modification

There will be no dose reductions. A vaccine administration can be withheld:

- At any time deemed appropriate, based on the best clinical judgment of the treating physician. Vaccine administration can be withheld for up to a week.
- For any Grade 2 increases in liver function tests, pancreatic function tests, or ANA titers, vaccine administration should be withheld until test results resolve to Grade 1 or baseline.
- The second vaccine administration can be withheld for up to one week and the third vaccine administration can be withheld for up to 2 weeks. These individuals will still be considered evaluable for the primary endpoint.
- If dose 2 is delayed by ≤ 1 week, dose 3 will still be scheduled at week 10. If dose 2 is not
 administered within 1 week of the scheduled time point, the participant will be considered "off
 agent" but will be followed per protocol. Dose 3 will not be given if dose 2 was not
 administered within the planned schedule.

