7.3 Evaluation During Study Intervention

Vaccine will be administered at Weeks 0, 2, and 10. Participants will be monitored for at least 30 minutes after each injection for possible emergent side effects.

Prior to vaccine administration:

- Females of childbearing potential will be required to document negative pregnancy test.
- Blood will be drawn for safety and/or immune response, as applicable (See Section 7.1 and see below).
- Adverse events and concomitant medications will be assessed (See Section 11.1 for details).
- Vital signs will be evaluated (temperature, blood pressure, heart and respiratory rates, and weight)
- Blood testing results will be reviewed by the treating physician for clinical significance and possible indications of toxicity.

Immune response will be tested at Weeks 2, 4, and 12. A repeat ANA titer will be drawn at Week 4. Blood tests to monitor toxicity will be conducted at Weeks 2, 4, 10, and 12. Urine cotinine will be monitored at Week 12.

Adverse events will be evaluated during all contacts with the participants, with emphasis on AE evaluation two weeks after each injection (See Section 11.1 for details). Possible adverse events and concomitant medication information will be captured by telephone at Weeks 16 and 20.

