13.4 Primary Objective, Endpoint(s), Analysis Plan

This pilot study is designed to evaluate the preliminary immunogenicity of the MUC1 vaccine (as assessed at Week 12) and the safety (assessed continually through Week 24) in individuals at high risk for developing lung cancer. The immune response to the vaccine will be evaluated by monitoring changes in IgG anti-MUC1 antibody titer ratio; defined as t12/t0, where t0 is the "initial titer" measured prior to vaccination, and t12 is the "final titer" drawn at 12 weeks. A titer ratio of ≥2 will be considered a positive response.

Immunogenicity of the MUC1 vaccine primary endpoint: The primary endpoint is the 12-week immunogenicity response where a response would be an antibody titer that is ≥2 fold higher at 12 weeks compared to baseline. The polyp trial showed a 44% response rate at week 12 compared to baseline. However, in this current study of individuals at high risk for lung cancer, we will enroll current and former smokers; thus, the population would be heterogeneous with potentially different immune response profiles. It is also likely that some spontaneous immunogenicity is generated. However, without a placebo arm, this is hard to estimate. We therefore hypothesize that around 40% of vaccinated participants will demonstrate a 2-fold or more increase in MUC1 titer at week 12 compared to pre-vaccination. A sample size of 40 evaluable participants will provide 96% power to detect an immunogenicity response rate of 15% versus 40% using a 2-sided test of proportions with a type I error rate of 0.05. With that same sample size of 40 evaluable participants, we also have sufficient power (83%) to detect an immunogenicity response rate of 20% versus 40% using a 2-sided test of proportions with a type I error rate of 0.05.

If the projected rates of screen failures and dropouts are overly optimistic, with 30 evaluable participants, we'd still have sufficient power for the primary endpoint. Specifically, a sample size of 30 evaluable participants will provide 90% power to detect an immunogenicity response rate of 15% versus 40% using a one-sided test of proportions with a type I error rate of 0.025. The primary analysis will be on all participants, without consideration of their baseline smoking status or MUC1 expression.

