13.6 Reporting and Exclusions

All registered participants who start treatment and complete both the baseline and 12-week post-baseline evaluation will be evaluable for the 12-week immunogenicity response primary endpoint using the modified intent-to-treat principle, as long as they received the Week 0, Week 2, and Week 10

injections (See Section 5.6 for delays in vaccine administration that are considered allowable and will not impact evaluability for the primary endpoint). We plan to over-accrue by about 20% overall to ensure an adequate sample size in the primary analysis cohort. There will be no imputation for missing data. A summary and listing of all major protocol violations will be provided. All details will be given in the final study report and/or manuscript. Participants lost to follow-up will be censored on the last date of assessment (or contact) and as appropriate for analyses that are dependent upon length of study participation. All eligible participants who start treatment will be evaluable for the safety

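### Dose 3 may be up to 2 weeks late with evaluability kept, but the Week 12 primary titer is not tied to the actual dose 3 date

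*Combined protocol and SAP*

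**What the plan says.** The third bullet of Section 5.6 states that "the third vaccine administration can be withheld for up to 2 weeks. These individuals will still be considered evaluable for the primary endpoint". Section 13.6 carries this into the analysis by referring back to 5.6 for "delays in vaccine administration that are considered allowable and will not impact evaluability for the primary endpoint".

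The titer itself runs on a calendar clock. Section 13.4 states that "t12 is the 'final titer' drawn at 12 weeks", and a ratio to baseline of at least 2 is a response. The Section 7.1 schedule puts dose 3 at Week 10 ± 4 days and the titer visit at Week 12 ± 4 days. Footnote 7 there places blood draws before the injection when both apply. Sections 13.6 and 13.8 require all three injections and a 12-week evaluation. Immunology blood is taken at screening and Weeks 2, 4, 12 and 24, so there is no titer between Week 4 and Week 12.

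The permitted delay is stated in three ways. The first bullet of 5.6 says "Vaccine administration can be withheld for up to a week". The third bullet gives 2 weeks for dose 3. Section 5.2 limits discretionary delay by reference to 7.1, where the Week 10 window is ± 4 days.

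**The concern.** The primary endpoint is meant to show the response to three injections: only participants who received all three count. If dose 3 slips and the draw does not, the time for dose 3 to act shrinks and can vanish. Section 2.2 reports that antibody in the earlier adenoma trial generally peaked after the third injection, so a draw taken too early would be expected to miss some responders. The plan deals with the knock-on effect of a late dose 2 (dose 3 stays at Week 10) but not with that of a late dose 3.

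A site that moves the draw departs from 7.1 and puts the participant's 12-week evaluation in doubt. A site that keeps the date may measure a titer from before the third dose. The two sites could act differently.

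The Week 12 rate feeds the decision on an efficacy trial (Section 3). With 40 evaluable participants, each one is 1/40 = 2.5 percentage points of that rate.

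**Working it through.** **Interval from dose 3 to draw.** Count days from the first injection. Nominal dose 3 is Day 70 (window 66–74) and the nominal draw is Day 84 (window 80–88). Let d be days late from Day 70.

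- On schedule, using both windows: 80 − 74 = 6 to 88 − 66 = 22 days.
- Late by d: from 80 − (70 + d) = 10 − d to 88 − (70 + d) = 18 − d days.
- d = 7: 3 to 11 days.
- d = 14: −4 to +4 days.
- Shorter than any on-schedule interval (under 6 days): possible when 10 − d < 6, so from d = 5; certain when 18 − d < 6, so from d = 13.
- Draw before dose 3, or on the same day and so before the injection: possible when 10 − d ≤ 0, so from d = 10.
- Week 24 draw (Day 168, window 161–175) after dose 3 on Day 84: 84 days nominal, 77 to 91.

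**The plan's own power.** One-sample normal approximation with n = 40 and z = 1.96:

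power = Φ{[(p1 − p0)√n − z√(p0(1 − p0))] / √(p1(1 − p1))}

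- 20% versus 40%: (0.20 × 6.325 − 1.96 × 0.400) / 0.490 = 0.98, giving 83.7% (plan: 83%).
- 15% versus 40%: (0.25 × 6.325 − 1.96 × 0.357) / 0.490 = 1.80, giving 96.4% (plan: 96%).

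**Illustration only.** The documents give neither the share of participants affected (f) nor their response rate (r). Both are assumed here, with everyone else responding at 40%. The overall rate is p = (1 − f) × 0.40 + f × r, and the mean number of responders lost is 40 × f × (0.40 − r). At r = 40% nothing is lost.

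| Affected, of 40 | r | Responders lost | Overall rate | Power vs 20% | Power vs 15% |
|---|---|---|---|---|---|
| 1 | 0% | 0.4 | 39.0% | 80.4% | 95.3% |
| 1 | 10% | 0.3 | 39.25% | 81.3% | 95.6% |
| 1 | 30% | 0.1 | 39.75% | 82.9% | 96.2% |
| 2 | 0% | 0.8 | 38.0% | 76.7% | 94.0% |
| 2 | 10% | 0.6 | 38.5% | 78.6% | 94.7% |
| 2 | 30% | 0.2 | 39.5% | 82.1% | 95.9% |
| 4 | 0% | 1.6 | 36.0% | 68.3% | 90.5% |
| 4 | 10% | 1.2 | 37.0% | 72.7% | 92.4% |
| 4 | 30% | 0.4 | 39.0% | 80.4% | 95.3% |

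**The case against.** The strongest reply is that the plan chose this on purpose. It defines the endpoint at 12 weeks and keeps allowed delays in a modified intent-to-treat set, and a Week 12 response under the permitted schedule is a coherent target. That is fair, but the plan also makes all three injections a condition of evaluability. A titer drawn before the third injection does not fit that condition.

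A second reply is that only the longest delays do harm. This stands. At one week late the draw is still 3 to 11 days after dose 3. Under the one-week limit in 5.6, or the ± 4 days reached through 5.2, no draw could precede dose 3. But 13.6 points to 5.6, whose bullet specific to dose 3 allows 2 weeks, so the gap remains until the limits are reconciled.

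A third is that sites would see participants two weeks after dose 3 anyway. Section 7.3 does ask for AE assessment "with emphasis on AE evaluation two weeks after each injection", but that concerns adverse events and does not move the titer.

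Fourth, delays may be rare: Section 2.2 reports nearly full compliance in the earlier trial. The effect in the table is also modest beside other choices. At 20% versus 40%, an exact binomial test has 78.9% power against 83.7% by the approximation. This stands too.

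A reader might infer more than the documents support:

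- **That every draw close to a late dose 3 is a two-dose titer.** This is certain only for draws before or on the day of the injection. For draws 1 to 4 days after it, a blunted response is an inference, because no onset time is given.
- **That the rule could produce a false claim of immunogenicity.** A titer taken too early is expected to lower the response rate.
- **That Week 24 offers no help because it is exploratory.** Section 1.3 lists it so, but 13.5 also uses the Week 24 ratio under the secondary objectives, for current versus former smokers. It partly mitigates the problem without entering the primary endpoint.
- **That the rate of abnormal liver tests in Section 6.2 (4 to 20 per 100) is a delay rate.** Grade 2 rises do require a hold under 5.6, but 6.2 gives no grades.

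**Conclusion.** The point holds, and it is minor. Followed as written, the plan can count a titer drawn before or on the day of dose 3 as a three-dose outcome. This becomes possible once dose 3 is 10 or more days late, and at the full 2 weeks the interval is −4 to +4 days against 6 to 22 on schedule.

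The expected bias is downward, and this rests on the earlier trial's report of peaks after dose 3. It will not affect every late participant. Some would not have responded anyway (56% did not in the earlier trial), and some may already have doubled after two doses.

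The size cannot be derived from the documents. Under the assumptions tabulated, one or two affected participants cost at most 0.8 responders on average and leave power against 20% at 76.7% or more. Section 3 sets no numerical threshold for proceeding, so no stated decision is shown to change.

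**What to change.** 1. **Analysis (13.6 and 13.8).** Report the dose-3-to-draw interval, taking the injection date from the Intervention Administration CRF. Before titers are analysed, prespecify one sensitivity analysis of the Week 12 response rate that excludes participants whose draw preceded dose 3 or fell less than 6 days after it. Six days is the shortest on-schedule interval, so no on-schedule participant is dropped. Show the Week 24 titer ratio for those excluded. The cost is a few lines of text, and no new data are needed.

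2. **Draw timing (7.1 and 13.4).** For participants not yet sampled whose dose 3 is late (after the Week 10 window closes on Day 74), time the primary research draw 14 ± 4 days from the actual third injection, and state that it counts as the 12-week evaluation. Leave on-schedule participants on the current window. Those already sampled are handled by item 1.

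   The new window is Day 80 + d to 88 + d. It overlaps the existing Day 80–88 window up to 8 days late; beyond that, a separate research-draw date is needed if the safety bloods keep theirs. Immunology draws are Monday to Thursday only, and any 9-day window holds at least four such days. After a full delay the draw falls on Day 94–102. Time from baseline is then up to about 2 weeks longer, and the timing departs slightly from that of the earlier 44% Week 12 benchmark.

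3. **Delay limits.** Sections 5.2 and 7.1 and the first and third bullets of 5.6 contradict each other. The sponsor must reconcile them; no dosing rule is proposed here.
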